## Study Methodology

- Study Description

- Design: Randomized controlled trial
- Blinding:
  - Blinded: Data analyst
  - Unblinded: patient, surgeon and anesthesiologist
- Location: Greenville Health System (Patewood Outpatient Hospital and Hillcrest Memorial Hospital)
- Sample size: Sample size estimates are based on the assumptions of a large clinical effect size (>.40) seen at 5 follow up points for the primary outcome measure of pain. Using a fixed effects, special, main and interactions, analysis of variance testing (ANOVA) with a power of 0.80 and an alpha of 0.05, we estimate the need for 86 subjects to achieve statistical significance. To account for loss of follow up, we will target 10% more subjects, thus 95 total participants.
- **Study population**
  - Subjects
    - Recruitment: Consecutive patients undergoing hip arthroscopy will be enrolled in the study
    - Inclusion criteria:
      - Scheduled for outpatient hip arthroscopy by [name]
      - ASA 1-3
      - Ages 18-65
    - Exclusion criteria:
      - Prior surgery on ipsilateral hip
      - ASA 4-6
      - Chronic narcotic usage over 6 months or more than the equivalent of 20mg of morphine per day
      - Current or prior placement of a spinal cord stimulator or intrathecal pump for pain control purposes
      - Allergy to amide local anesthetics
      - Contraindication to regional anesthesia
      - BMI > 40
      - Females who are pregnant or plan to get pregnant during the course of the study

- **Study procedure**

At the pre-operative clinic appointment, patients will be recruited into the study. Informed consent will be obtained from the patient by the study doctor. The nature of the experiment will be explained, specifically that the patient agrees to be randomized to receive a block prior to the operation or to receive the joint injection at the conclusion of the surgery as an adjunct to general anesthesia. If the patient agrees to enter into the study, the patient will be randomized by use of a computer generated randomization program at the time of enrollment in the clinic. Currently, the standard of care at the Steadman Hawkins Clinic of the Carolinas is to offer surgical patients a block as an analgesic option. Fl blocks are not ordered by the doctor without a request by the patient. If patients do not receive a Fl block, they will receive a local anesthetic intraoperatively by the surgeon at the close of the procedure, which is also currently the standard of care for hip surgery.

On the day of surgery, all patients will receive multimodal analgesia with an oral preoperative cocktail consisting of acetaminophen 15mg/kg up to a maximum of 1000mg, celebrex 400mg, lyric 75mg, and oxycontin 10mg unless they are allergic to any of the components. Both block (B) and non-block (NB) patients will receive pre-operative midazolam 1-5 mg as needed for procedural sedation (B) or pre-operative anxiety (NB) respectively.

Patients to be blocked will receive not less than 50 ml and up to 60 mL of 0.35% ropivacaine at a dose of 3 mg/kg (with adjuvants of 100 mcg clonidine [per 60 mL] and epinephrine 1:400,000) placed using a 17 gauge 3.2" B-Braun Tuohy needle under ultrasound guidance using a SonoSite S-Nerve machine with a 15-10 MHz 38 mm probe using a caudad to cephalad in-plane approach. (A 70kg patient would receive all 60 mL of the block solution and 210mg of ropivacaine total). The blocks will be placed exclusively by a selected group of anesthesiologists, who have been trained in the technique.

Patients who are randomized to no-block will receive a single injection of Noropin in the joint space.

General anesthesia will be conducted in a standard fashion for all patients. General anesthesia with an endotracheal tube will be induced with IV fentanyl 2 mcg/kg, lidocaine 50mg, propofol 2 mg/kg, and rocuronium 0.6 mg/kg unless another plan is chosen at the discretion of the attending anesthesiologist. Maintenance of anesthesia will be done with O2:air FIO2 50%, isoflurane end-tidal concentration of 0.7-1.4%, and tidal volumes of 7-10 mL/kg with a respiratory rate to maintain an end-tidal carbon dioxide concentration of 30-40 mmHg. Fentanyl will be given in 25-50 mcg increments for HR or BP greater than 20% over baseline. No long acting intra-operative opioids will be administered and only fentanyl will be used. Ephedrine in 5-10 mg increments or neosynephrine in 80-160 mcg increments will be used to treat hypotension at the anesthesiologist's discretion. A minimum of 20mL/kg of IV crystalloid will be administered during the surgery. Ondansetron 4 mg IV will be administered to all patients approximately 30 minutes prior to emergence for PONV prophylaxis.

Post-operatively in the recovery room, hydromorphone will be used as a first line opioid for pain given in 0.2-0.5 mg increments to an initial maximum of 4 mg. Nausea will be treated in a stepwise fashion with promethazine 6.25 mg IV as a first line agent. Second line will be a repeat dose of promethazine 15 minutes after the first dose, followed by diphenhydramine 6.25 mg IV 15 minutes later PRN. Pain scores will be recorded initially upon arrival to the PACU and thereafter until the patient is discharged from the PACU. All episodes of nausea and vomiting will be tallied. Total recovery time in the PACU will be recorded. If a patient is otherwise ready for discharge but remains in the PACU due to a non-medical issue (i.e. bed hold), the time at which the patient could have otherwise been discharged will be

recorded as the PACU end time for the purposes of the study. Any unplanned admissions will be noted. All opioids administered intraoperatively and in the PACU will be recorded and converted to morphine equivalents.

Patients will be followed in the study surgeon's clinic office per his standard protocol at 2 weeks, 6 weeks, and 3 months post-operatively. Pain scores will be evaluated at this time. Clinical outcome measures and range of motion of the patients' hips will be collected at this time as well. Any adverse reaction from the block will be noted and recorded at all times from the administration of the block and at each clinic follow up. Any signs or symptoms of numbness in the distribution of the fascia iliaca block will be noted.

- Primary endpoint: Quantify the difference in pain in patients who have received a pre-operative FI block versus those receiving no block.
  - Secondary endpoint: Quantify the difference in opioid consumption in patients who have received a pre-operative FI block versus those receiving no block.
  - Tertiary endpoints: Assess differences in episodes of PONV, time in PACU, and proportion of unplanned admissions
- Risks / benefit
  - Risks associated with FI blocks are the following:

Overall the procedure has a very low risk profile. The location of the injection means the risk of intravascular injection, local anaesthetic toxicity, and mechanical nerve damage is extremely low.

Good aseptic technique will minimize the risk of infection. The injection of a large volume of local anaesthetic ensures good spread and reduces the risk of failure. The risk of local anaesthetic toxicity is highest within the first 15 minutes after injection, which makes close monitoring mandatory.
  - The potential benefit is improvement in pain control and opioid consumption in FI patients. The knowledge gained from this study will also be used in future patients with this condition.

- **Statistical Analysis**

The study incorporates four dedicated follow up points beyond baseline: a) perioperative (1 to 5 days), b) 2 weeks, c) 6 weeks, and d) 3 months. The primary outcome measure (pain) will be analyzed using a fixed effects, special, main and interactions, analysis of variance testing (ANOVA). Opioid consumption will be analyzed using a Pearson chi square or parametric equivalent (depending on final coding). Tertiary end points will be captured using an ANOVA for continuous measures (once tests of normality are completed), or Kruskal Wallis, whereas re-admission rates will be analyzed using a Pearson Chi-square. A p value of 0.05 will be considered statistically significant for all findings. Intention to treat and last value carried forward will be integrated for all analyses.

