- Hypothesis: Pre-operative placement of an ultrasound-guided fascia iliaca block in patients undergoing hip arthroscopy will result in reduced pain scores and opioid consumption compared to patients receiving an opioid-only regimen.
  - Secondary hypothesis: Pre-operative placement of an ultrasound-guided fascia iliaca block in patients undergoing hip arthroscopy will result in fewer episodes of PONV, reduced time in PACU, and lower rates of unplanned admissions compared to patients receiving an opioid-only regimen.

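### The 86-subject figure at 80% power fits an ANOVA term over six pain time points, but the analysis plan has at most five and names no tested term

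*Combined protocol and SAP*

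**What the plan says.** Under Sample size in Study Methodology, the calculation rests on a "large clinical effect size (>.40) seen at 5 follow up points for the primary outcome measure of pain". It uses a fixed-effects ANOVA with main effects and interactions, power 0.80 and alpha 0.05, and concludes: "we estimate the need for 86 subjects to achieve statistical significance". Ten percent is added for loss to follow-up, giving 95. The Protocol Summary describes two arms.

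Under Statistical Analysis, pain is to be analysed by the same type of ANOVA, again with no tested term named. The visit count differs: "The study incorporates four dedicated follow up points beyond baseline", listed as "a) perioperative (1 to 5 days), b) 2 weeks, c) 6 weeks, and d) 3 months".

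The hypothesis in Introduction / Background is a between-arm one: the block "will result in reduced pain scores and opioid consumption compared to patients receiving an opioid-only regimen".

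On when pain is measured, the Schedule of Events marks VAS at baseline, 2 weeks, 6 weeks and 3 months, and not at the procedure. The Study procedure text says of recovery: "Pain scores will be recorded initially upon arrival to the PACU and thereafter until the patient is discharged from the PACU". Clinic follow-up is then "per his standard protocol at 2 weeks, 6 weeks, and 3 months post-operatively".

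**The concern.** A power statement is useful only if it refers to the test that will be run. Here the metric, the term and the degrees of freedom are all left out, and the number of follow-up points is five in one section and four in another. Because the 80% is not tied to the term that tests the between-arm hypothesis, a reader cannot tell what arm difference a null result would make unlikely.

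Two related gaps concern the same outcome. The sizing formula counts each subject as one independent observation, and the ANOVA as described has no patient term, although the same patients give pain scores at several visits. The earliest analysed pain point, at 1 to 5 days, also has no described collection.

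**Working it through.** **Inputs from the documents.** Effect size above 0.40; alpha 0.05; power 0.80; N = 86; two arms; five follow-up points (Sample size) or four beyond baseline (Statistical Analysis).

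**Assumption.** 0.40 is Cohen's f, evaluated at the stated bound.

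**Formula.** For a fixed-effects ANOVA, power = P[F′(df1, df2, λ) > F₀.₉₅(df1, df2)], where F′ is noncentral F, λ = N f² and df2 = N − number of cells. At N = 86 and f = 0.40, λ = 86 × 0.16 = 13.76. With two arms, group has 1 df. Time and group-by-time over k time points each have k − 1 df, with 2k cells.

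**Reproducing the plan's figures.** With df1 = 5 the smallest N reaching 80% is 86 with 6 or 7 cells (power 80.1% with 6 cells), and 87 with 8 to 12 cells. No other numerator df gives 86 at alpha 0.05. The allowance also reproduces: 86 × 1.10 = 94.6, rounded up to 95.

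**Each term of a two-arm design, f = 0.40:**

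| Term | df1 | Cells | N for 80% | Power at N = 86 | f at which required N is 86 |
|---|---|---|---|---|---|
| Group | 1 | 2 | 52 | 95.6% | 0.306–0.307 |
| Time or group-by-time, 4 time points | 3 | 8 | 73 | 87.3% | 0.365–0.367 |
| Same, 5 time points | 4 | 10 | 80 | 83.5% | 0.384–0.387 |
| Same, 6 time points | 5 | 12 | 87 | 79.8% | 0.401–0.403 |

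The first three rows cover the Statistical Analysis plan: four follow-ups, or five time points if baseline is a level. The last row is the Sample size count of five follow-ups plus baseline.

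**Does it depend on f being exactly 0.40?** Not for the first three rows. Each gives 86 only at an f below 0.40, and a larger f needs fewer subjects (at f = 0.45: 41, 59 and 65). The six-point row gives exactly 86 at an f just above 0.40, which satisfies the protocol's inequality.

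**Other readings of 0.40.** As Cohen's d it needs 198 to 199 subjects in total; as f², 22 to 49; as eta-squared, 14 to 33. A repeated-measures ANOVA with f = 0.40 and four to six time points needs 11 to 51 for the group term (correlation 0 to 0.99) and at most 19 for the interaction. None gives 86.

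**Why the choice of term matters (illustration only).** Assume 43 per arm, four follow-ups, compound symmetry and within-patient correlation ρ of 0.2, 0.5 or 0.8; the documents give none of these. All differences are in per-visit SD, at 80% power.
- Averaged between-arm test, constant difference: 0.611 × √((1 + 3ρ)/4) = 0.39, 0.48, 0.56.
- Same test, effect at one visit only: four times as large, 1.55, 1.93, 2.25.
- Group-by-time test, effect δ at one visit only: λ = 43 × 0.375 × δ²/(1 − ρ), df 3 and 252, giving δ = 0.74, 0.59, 0.37.

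**Pain time points side by side.** Statistical Analysis uses 1 to 5 days, 2 weeks, 6 weeks and 3 months. The Schedule of Events has no VAS between baseline and 2 weeks. The Study procedure text records pain in the PACU until discharge and next at the 2-week clinic visit. No section says how or when a 1-to-5-day score is obtained.

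**The case against.** The strongest reply is that the sample-size paragraph is consistent with itself. Its five follow-up points plus baseline make six time points, so group-by-time has 5 df. That needs 87 subjects at f = 0.40 and exactly 86 at about 0.401 to 0.403. The five points can even be assembled from the documents: the PACU scores plus the four follow-ups listed under Statistical Analysis, with the baseline VAS as the sixth level. This stands as a plausible account, although it is an inference because no section lists the five.

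A reader might infer from the table that no term of a two-arm ANOVA yields 86, and that the protocol made an arithmetic slip. The documents do not support that. They show two sections working from different visit counts. If five was instead meant loosely, as baseline plus four, the interaction has 4 df and the gap is small: 80 against 86 subjects, or 83.5% against 80%.

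It is also fair to say that the metric is inferred, that the correlation illustration rests wholly on assumed values, and that for every term on the Statistical Analysis plan 86 exceeds the computed requirement. All of that stands. It limits the point to one of consistency and traceability. It does not supply the missing term, nor reconcile the sections.

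**Conclusion.** The concern holds as an inconsistency in the stated basis for power. With 0.40 read as Cohen's f, 86 subjects at 80% matches 5 numerator df and hence six time points, while the Statistical Analysis section plans at most five. On that plan the same formula gives 86 subjects about 95.6% (group), 87% (3 df) or 83.5% (4 df), so the stated 80% describes none of its terms.

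A reader might also infer that the trial is underpowered. That does not follow: within this formula the misstatement is conservative. Whether 86 is enough under a proper repeated-measures calculation cannot be judged until the term, time points and correlation range are stated.

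The neglect of within-patient correlation, in both the sizing formula and the ANOVA as described, and the unscheduled 1-to-5-day score hold whatever metric was meant. Confidence in the df mismatch is moderate, because both the metric and the 5 df are inferred from the arithmetic. The change should be made, since it is cheap and needs no more patients.

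**What to change.** 1. List the pain time points once and use that list in the Schedule of Events, Sample size, Study procedure and Statistical Analysis. Either schedule the 1-to-5-day score, saying how it is collected, or replace it with the PACU score that is already recorded.
2. Name the term that tests the between-arm pain hypothesis, with its df, effect-size metric and allocation ratio, in a repeated-measures analysis.
3. Restate the power or detectable difference of 86 evaluable subjects for that term over a stated range of within-patient correlations.

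Suggested wording, with blanks for the sponsor:

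> The primary test is the [term, df] in a repeated-measures analysis of pain at [time points]. With 86 evaluable subjects allocated [ratio], power is [value] at two-sided alpha 0.05 to detect [effect, metric], assuming [pattern over visits], [correlation structure] and within-patient correlations of [range].

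Leave the target of 95 unchanged; this point gives no reason to alter it. The cost is a rewritten sample-size paragraph, an aligned schedule and a decision on the term, time points and correlation range. The stated power or detectable effect may change as a result.

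### Eligible patients differ in pre-operative opioid use, but the plan specifies no baseline record of it and compares perioperative opioid consumption with an unadjusted test

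*Combined protocol and SAP*

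**What the plan says.** All references are to the combined protocol and SAP.

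- **Eligibility** (Study Methodology, exclusion criteria): patients are excluded for "Chronic narcotic usage over 6 months or more than the equivalent of 20mg of morphine per day". The text does not define chronic use, say whether that word governs the dose limit, or give a period over which the dose is judged.
- **Baseline data** (Schedule of Events): the baseline column lists consent, the eligibility check, range of motion and VAS pain. There is no separate item for current opioid use.
- **Allocation** (Study procedure): "the patient will be randomized by use of a computer generated randomization program at the time of enrollment in the clinic". No stratification factor is mentioned.
- **Endpoint**: the plan gives "Secondary endpoint: Quantify the difference in opioid consumption in patients who have received a pre-operative FI block versus those receiving no block". The Introduction also places opioid consumption within the primary objective.
- **Measurement** (Study procedure): "All opioids administered intraoperatively and in the PACU will be recorded and converted to morphine equivalents".
- **Analysis** (Statistical Analysis): "Opioid consumption will be analyzed using a Pearson chi square or parametric equivalent (depending on final coding"). The pain analysis is a fixed-effects ANOVA, and no opioid term is named for it either.

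**The concern.** The opioid endpoint is a total dose given in theatre and recovery. How much a patient was already taking beforehand is a plausible predictor of that total, and the sponsor treats prior use as relevant by excluding heavier or longer users. Applying the exclusion means asking about dose and duration, so the information is close to hand before allocation.

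The plan does not say that the answer is kept as a variable, and the stated test cannot use it. Two things are at stake. First, variation between patients that could be explained stays in the error term. Second, if the arms happen to differ in prior users, there may be no recorded value with which to adjust. In a trial of 95 patients neither is negligible if prior use is common and predictive.

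**Working it through.** **1. Who is admitted.** Three readings of the exclusion were compared. The second needs a definition of chronic, assumed here to be at least 3 months.

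| Pre-operative use | Either limit excludes | Chronic governs both limits | Both limits must be exceeded |
|---|---|---|---|
| None | admitted | admitted | admitted |
| 10 or 20 mg/day for 1, 3 or 6 months | admitted | admitted | admitted |
| 25 mg/day for 1 month | excluded | admitted | admitted |
| 10 mg/day for 7 months | excluded | excluded | admitted |

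The first two rows do not depend on the reading: naive patients and daily users are enrolled together in every case. The last two rows show where the wording matters.

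**2. The plan's own figure.** The sample size assumes a "large clinical effect size (>.40) seen at 5 follow up points for the primary outcome measure of pain" and, "with a power of 0.80 and an alpha of 0.05, we estimate the need for 86 subjects to achieve statistical significance". Reading 0.40 as Cohen's f, the non-central F calculation uses noncentrality N × f². The numerator degrees of freedom are not stated; 5, with 2 to 6 groups, gives exactly 86 (power 0.801 to 0.802). Then 86 × 1.10 = 94.6, so 95. The figure reproduces, but it is for pain. No power is stated for opioid consumption, so no corrected sample size follows from this point.

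**3. Precision.** For a continuous outcome and a baseline covariate with correlation r, the residual variance is multiplied by (1 − r²), which is worth a factor 1/(1 − r²) in patients. The documents give no r.

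- r = 0.2: 1 − 0.04 = 0.96; 1/0.96 = 1.04, or 4% more patients
- r = 0.3: 1 − 0.09 = 0.91; 1/0.91 = 1.10, or 10% more
- r = 0.5: 1 − 0.25 = 0.75; 1/0.75 = 1.33, or 33% more

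As an illustration only, take 43 per arm (86/2, equal allocation assumed) and a true difference of 0.5 SD (assumed). Power is Φ(0.5 × √(43/2) / √(1 − r²) − 1.96). This gives 64% unadjusted, 68% at r = 0.3 and 76% at r = 0.5.

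**4. Chance imbalance.** Let p be the proportion of enrolled patients using any opioid (not in the documents; 15% to 35% assumed), with arms of 47 and 48. The SD of the between-arm difference is √(p(1 − p)(1/47 + 1/48)).

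| p | SD of difference | Chance of a gap of 10 points or more (normal approximation) |
|---|---|---|
| 0.15 | 0.073 | 17% |
| 0.25 | 0.089 | 26% |
| 0.35 | 0.098 | 31% |

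**5. What a 10-point gap does.** Treating use as yes or no, the shift in the opioid comparison is 0.10 × r/√(p(1 − p)) outcome SDs.

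- Smallest (r = 0.3, p = 0.35): 0.10 × 0.3/0.477 = 0.06 SD
- Largest (r = 0.5, p = 0.15): 0.10 × 0.5/0.357 = 0.14 SD

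The standard error of the unadjusted comparison is √(1/47 + 1/48) = 0.205 SD. The shift is therefore about 0.3 to 0.7 of a standard error.

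**The case against.** The strongest reply is that randomisation balances prior use in expectation and that the error rate of an unadjusted test already allows for chance imbalance. That is right, and step 5 agrees: a 10-point gap moves the estimate by less than one standard error. What remains is a precision argument.

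The assumed correlation may also be generous. With 15% to 35% users, r = 0.5 implies that users consume about 1.2 to 1.6 within-group SDs more than non-users (0.5/0.477/0.866 and 0.5/0.357/0.866), although on the plain reading the exclusion caps use at 20 mg a day. Part of the outcome is driven by the anaesthetic protocol: fentanyl is given by body weight at induction and then in response to heart rate or blood pressure. That part need not follow prior use. This stands as a reason to treat the 33% as an upper figure within the assumed range.

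Admitting low-dose users is a legitimate pragmatic choice. That a low-dose, long-duration user can be excluded while a higher-dose, shorter-duration user is admitted follows from any rule with two separate limits and is not a defect. The plain reading, in which either limit excludes, is also the most natural, so the ambiguity is modest.

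None of this removes the point that a cheap, pre-allocation predictor is neither specified as data nor used.

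**Conclusion.** The point holds as a low-cost improvement to the secondary endpoint. On any reading the trial mixes opioid-naive patients with daily users, the plan specifies no baseline opioid variable, and the stated opioid test is unadjusted. If r is 0.3 to 0.5, adjustment is worth 10% to 33% more patients; if r is lower the gain is small, and at r = 0 it is nil. Both r and the prevalence of prior use are assumptions.

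A reader might infer more, and the documents do not support it:

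- **That the opioid comparison is biased.** Allocation is random, so any difference in prior users arises by chance.
- **That the randomisation is unstratified, or that the screening value is thrown away.** The text is silent on both; not specified is the accurate description.
- **That two sites will apply the exclusion differently.** Two hospitals are listed as locations, but inclusion is limited to one surgeon's patients, with enrolment and randomisation in the clinic. Inconsistent application from patient to patient remains possible.
- **That adjustment would raise the planned 80% power to some higher figure.** The 80% belongs to the pain ANOVA.

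**What to change.** 1. Add a baseline field for current daily opioid dose in morphine equivalents, taken from the eligibility check and recorded before randomisation. Define it as the patient's own use before the study, separate from the oral opioid that the protocol gives on the day of surgery.
2. Analyse total intraoperative plus PACU morphine equivalents as a continuous outcome by ANCOVA or linear regression, with treatment arm and the baseline dose as prespecified terms. This replaces the Pearson chi-square, which cannot take a covariate. Fix in advance the form of the covariate (dose, or any versus none if most values are zero) and any transformation of the outcome.
3. State whether duration and dose are separate grounds for exclusion or must be met together, whether chronic applies to both, and over what period the dose is judged. The limits themselves are for the sponsor; none is proposed here.

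Stratifying the randomisation by any versus no use is optional; the recorded covariate brings most of the benefit. The cost is one data field, one model term (one residual degree of freedom) and a clarification of the eligibility wording. The sample size is unchanged.

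### Randomizing at the pre-operative clinic, with unblinded patients and a block obtainable on request in usual care, leaves an avoidable window for arm-driven withdrawal, cancellation and some switching

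*Combined protocol and SAP*

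**What the plan says.** All of this is in the combined protocol and SAP, under Study Methodology unless noted.

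- **Timing of randomization (Study procedure).** After consent at the pre-operative visit, "the patient will be randomized by use of a computer generated randomization program at the time of enrollment in the clinic". Treatment belongs to a separate, later day, introduced by "On the day of surgery, all patients will receive multimodal analgesia". The length of the gap is not given.
- **Blinding.** "Unblinded: patient, surgeon and anesthesiologist". Only the data analyst is blinded, so the single-blind label in the Protocol Summary does not shield the patient from the assignment.
- **Usual care (Study procedure).** Practice at the clinic "is to offer surgical patients a block as an analgesic option", and "Fl blocks are not ordered by the doctor without a request by the patient". For patients without a block, "they will receive a local anesthetic intraoperatively by the surgeon at the close of the procedure, which is also currently the standard of care".
- **Analysis (Statistical Analysis).** "Intention to treat and last value carried forward will be integrated for all analyses". The endpoints, by contrast, are worded by whether a block was received.
- **Schedule of Events.** Consent, eligibility and VAS share the baseline column. A surgical-details entry is made at the procedure.

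No section says when the patient is told the arm, how a departure from assignment is handled in the data, or that such a departure must be recorded.

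**The concern.** Neither treatment has to be fixed at the clinic visit: the block is placed before the operation and the joint injection is given at its end. Early assignment to an unblinded patient therefore opens an interval in which knowledge of the arm can affect behaviour. A control patient may prefer the block that usual care would provide on request. A patient assigned to the block may decide against it. Either may withdraw or cancel surgery.

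These routes do different harm:

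- **Switching** pulls the assigned arms together under intention to treat.
- **Leaving before surgery** costs information, and can bias the comparison if it differs by arm. Under last value carried forward, the only pain value available is the baseline VAS, which was taken before any treatment.
- **Analysing by block received**, as the endpoint wording might suggest, would exchange dilution for selection bias, because those who switch choose to do so.

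**Working it through.** **Inputs.** From the Sample size item: effect size 0.40 (read as Cohen's f, since the text calls it large and above .40), alpha 0.05, power 0.80, 86 subjects, raised by 10% to 95. The numerator df of the ANOVA is not stated. The documents give no crossover rate, so c below is an assumed range.

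**1. Reproduce the plan's figure.** Power = P[F′(df1, df2, λ) > F(0.95; df1, df2)], where F′ is the noncentral F, λ = f²N and df2 = N − number of cells. At N = 86, λ = 0.16 × 86 = 13.76.

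- df1 = 5 needs N = 86 with 2 to 6 cells, or 87 with 8 to 12 cells.
- df1 = 4 (the interaction of 2 arms with 5 occasions) needs 80.
- df1 = 1 (arm main effect) needs 52.

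So 86 corresponds to df1 = 5. Then 86 × 1.10 = 94.6, rounded up to 95.

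**2. Dilution from switching.** Let c be the fraction of controls who get a block plus the fraction of block patients who do not. If a switched patient shows the full effect of the treatment received, the intention-to-treat difference is (1 − c) times the true one, so f becomes 0.40(1 − c). For example, c = 0.10 gives f = 0.36 and λ = 0.1296 × 86 = 11.15.

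| Net crossover c | f | Power at 86, df1 = 5 (10 cells) | N for 80%, df1 = 5 | Power at 86, arm main effect | N for 80%, main effect |
|---|---|---|---|---|---|
| 0 | 0.40 | 0.80 | 87 | 0.96 | 52 |
| 5% | 0.38 | 0.75 | 95 | 0.94 | 57 |
| 10% | 0.36 | 0.70 | 105 | 0.91 | 63 |
| 20% | 0.32 | 0.58 | 132 | 0.83 | 79 |
| 30% | 0.28 | 0.45 | 170 | 0.73 | 103 |

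With df1 = 5, about 5% net crossover uses the whole margin from 86 to 95, which the plan assigns to loss to follow-up. For the main effect, 86 still gives more than 80% power at 20%.

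**3. Patients who leave before surgery.** Let fractions w_B (block) and w_C (control) leave, with mean baseline VAS b carried forward, and let m_B and m_C be the arm means of those treated. If those who leave are otherwise typical, the estimated difference is (1 − w_B)m_B + w_B·b − (1 − w_C)m_C − w_C·b.

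- If w_B = w_C = w, this is (1 − w)(m_B − m_C): dilution by w.
- If only controls leave (w_B = 0), it is (m_B − m_C) + w_C(m_C − b): a bias whose sign depends on whether treated controls report more or less pain than at baseline.

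If those who leave are instead dropped from the analysis, the loss is in numbers. Losing 20% of 95 leaves 76 and power of about 0.73 with df1 = 5.

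**The case against.** The strongest reply is that every patient consents to be assigned to either treatment before being randomized, and the protocol fixes what a no-block patient receives. The request route describes current practice and is not an entitlement within the trial. This stands as a mitigation. It lowers the risk, but it does not bind a patient who later learns the arm, and the plan has no way of showing whether departures occurred.

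Several stronger readings are tempting, and the documents do not support them:

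- **That patients are told their arm at the clinic.** The text says when the program is run and that patients are unblinded. It does not say when the result is disclosed.
- **That crossover will occur at some known rate.** No rate, and no instance, is documented.
- **That the stated 80% power falls to 0.76, 0.71, 0.61 and 0.50 at 5, 10, 20 and 30% crossover.** Those values come from Φ(2.80(1 − c) − 1.96), a one-df approximation anchored at 80%. The plan's 86 is not a one-df calculation: with one df at f = 0.40 it starts at 0.96.
- **That the 10% margin excludes cancellations.** A patient cancelled after randomization could reasonably be counted as lost to follow-up. The margin does not cover switching.
- **That knowing the arm distorts the baseline VAS.** Nothing requires the score to come before disclosure, but the endpoint is pain between arms, not change from baseline, so this is speculative.
- **That later randomization would end switching.** An unblinded patient could still ask for or decline a block that day.

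Early assignment also has a practical use: there are two hospitals, and only selected anesthesiologists place the blocks.

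**Conclusion.** The point holds as a design weakness worth correcting, not as a demonstrated bias. Randomization at the clinic, treatment on a later day, an unblinded patient and a block available on request in usual care are all in the text. That the arm becomes known at the clinic is an inference, though the natural one.

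The power cost depends on two things the documents leave open: the amount of net crossover and the numerator df. At 10% it ranges from modest (0.96 to 0.91 for the arm main effect) to material (0.80 to 0.70 with 5 df). Whatever the df, the estimated effect shrinks in proportion to net crossover, and arm-related withdrawal can bias it. These figures assume f = 0.40, unchanged variability and full treatment effect in those who switch.

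**What to change.** 1. In Study procedure, keep consent, eligibility and baseline VAS at the clinic visit. Move the run of the same computer program to the day of surgery, after eligibility and willingness to accept either arm are reconfirmed and before sedation.
2. If scheduling the trained anesthesiologists requires earlier assignment, allow it, but keep the assignment concealed from the patient until that day.
3. On the surgical-details form already in the Schedule of Events, record the treatment actually received and the reason for any departure from assignment. Record withdrawals and cancellations after randomization by arm, with reasons.
4. State in Statistical Analysis that the comparison is by assigned arm, and align the endpoint wording with it.

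The cost is a wording change, running the program on a different day and a few added data items. The real downside is that a trained anesthesiologist must be available on each participant's surgery day before the arm is known; option 2 avoids this. The change shortens the window for arm-driven departures without closing it, and the added recording makes what remains measurable.
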